9.6.3. Secondary Outcome Analysis

1. Diagnostic accuracy metrics. Sensitivity, specificity, positive predictive value (PPV), and negative predictive value (NPV) of LaserSAFE image interpretation will be calculated with corresponding two-sided 95% confidence intervals. These will be reported in two ways:
 - a. For detection of any positive surgical margin (PSM), regardless of length, compared with FFPE analysis.
 - b. For detection of PSMs greater than 3 mm, compared with FFPE analysis.
Two-sided 95% confidence intervals will be calculated using the Wilson score method.
2. Descriptive outcomes. The following will be summarised using descriptive statistics (means, proportions, and 95% confidence intervals as appropriate):
 - a. Rate of residual prostate cancer in secondary resections of the neurovascular bundle.
 - b. Prevalence of PSMs detected by paraffin analysis in the overall cohort.
 - c. Prevalence of biochemical recurrence or salvage treatment for prostate cancer within 12 months post-surgery.
 - d. Mean scores for the EPIC-26 urinary incontinence and erectile function domains at baseline, 3 months, and 12 months post-surgery.

10. ASSESSMENT AND MANAGEMENT OF RISK

Intervention	Potential risk	Risk Management
LaserSAFE procedure	Time delay to finalise surgery False negative result which results in positive margin	Performed by trained personnel to minimize time delay. Follow standard operational procedure. Previous experience with the LaserSAFE technique has shown high accuracy and safety of the procedure. From NeuroSAFE PROOF study 200 NeuroSAFE procedures with 0 adverse reactions using a similar intervention.

11. RECORDING AND REPORTING OF ADVERSE EVENTS

11.1. Definitions

Term	Definition
Adverse Event (AE)	Any untoward medical occurrence in a patient or trial participant, which does not necessarily have a causal relationship with the intervention involved.
Serious Adverse Event (SAE).	Any adverse event that: 
• results in death,• is life-threatening*,• requires hospitalisation or prolongation of existing hospitalisation**,• results in persistent or significant disability or incapacity, or• consists of a congenital anomaly or birth defect.• Other 'important medical events' may also be considered serious if they jeopardise the participant or require an intervention to prevent one of the above consequences

* A life- threatening event, this refers to an event in which the participant was at risk of death at the time of the event; it does not refer to an event which hypothetically might have caused death if it were more severe.
 
** Hospitalisation is defined as an in-patient admission, regardless of length of stay. Hospitalisation for pre-existing conditions, including elective procedures do not constitute an SAE.
	

11.2. Assessments of Adverse Events

Each adverse event (AEs) will be assessed for severity, causality, seriousness and expectedness from consent to 90 days post op as it unlikely any SAEs past this point will be related to surgery. Adverse event assessment will be carried out using the patient electronic clinical records. This will reduce site reporting workload. Trial follow up should continue according to schedule once the SAE is resolved, if applicable.

11.2.1. Severity

Category	Definition
Mild	The adverse event does not interfere with the participant's daily routine, and does not require further intervention; it causes slight discomfort

Moderate	The adverse event interferes with some aspects of the participant's routine, or requires further intervention, but is not damaging to health; it causes moderate discomfort
Severe	The adverse event results in alteration, discomfort or disability which is clearly damaging to health

11.2.2.Causality

Although in previous studies no evidence of adverse events related to real time analysis of surgical margins using NeuroSAFE has been found. We will still monitor and assess relationship of adverse events. The differentiated causality assessments will be captured in the trial specific CRF SAE form.

The following categories will be used to define the causality of the adverse event:

Category	Definition
Related	A causal relationship between the intervention and an adverse event is at least a reasonable possibility, i.e., the relationship cannot be ruled out.
Not related	There is no reasonable possibility of a causal relationship between the intervention and an adverse event.
Not Assessable	Unable to assess on information available.

11.2.3.Expectedness

All SAEs assigned by the Investigator or delegate as suspected to be related to the intervention will be assessed for expectedness against the list defined in this protocol.

Category	Definition
Expected	An adverse event which is consistent with the information about the intervention clearly defined in this protocol.
Unexpected	An adverse event which is not consistent with the information about the intervention or clearly defined in this protocol.

The following are expected adverse events following a radical prostatectomy with their corresponding likelihoods. These should be recorded in the patient's medical records but do not need an Adverse Event CRF to be submitted. These will be recognised as expected for trial treatment.

- **Intra-operative**
 - Bleeding – (requiring transfusion) - 1%
 - Visceral injury requiring laparotomy – 1%
 - Vascular injury requiring laparotomy – 1%
 - Cardiac event (Myocardial infarction 0.1%, Atrial Fibrillation 1.6%, syncope 1.2%).
- **Early post-operative**
 - Wound related problems; infection (2%), incisional hernia (2%)
 - Thromboembolic event (deep vein thrombosis or pulmonary embolus 0.8%)
 - Lymphoedema – 1% (higher incidence when eLND performed)
 - Anaesthetic problems requiring admission to intensive care unit (2%)
 - Gastrointestinal; ileus/damage to bowel requiring temporary colostomy (0.5%)
 - Seroma – 1%
 - Urethral Stricture – 2%
 - Vesicourethral anastomosis leak – 5%
- **Expected longer term outcomes or side effects of surgery**
 - Urinary incontinence (temporary) – 100%
 - Erectile dysfunction – (up to 100%)
 - Long term urine leak – 10%
 - Adjuvant therapies (including radiotherapy and ADT) – 30%

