11.2.4. Recording of Adverse Events

All adverse events will be recorded in the medical records in the first instance. Expected adverse events related to RARP listed above will not require reporting. All related adverse events will be recorded in the CRF until 90 days after surgery.

All related adverse events will also be recorded on the non-CTIMP Adverse Event (AE) log, and stored in the site files.

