11.3. Procedures for Recording and Reporting Serious Adverse Events (SAEs)

All serious adverse events related to the intervention will be recorded in the medical records and the CRF, and the sponsor's SAE log. The AE and SAE logs will be stored in the TMF Investigator Site File and may be subject to Sponsor monitoring and auditing.

Participants will be followed up until clinical recovery is complete and laboratory results have returned to normal or baseline values, or until the event has stabilised. Follow-up will continue after completion of protocol treatment and/or trial follow-up if necessary.

All SAEs (except those specified in the protocol as not requiring reporting to the Sponsor) will be reported to the Sponsor within 24 hours of becoming aware. The CI/PI or designated individual will complete the Sponsor's online Research Incident Reporting Form (<https://redcap.slms.ucl.ac.uk/surveys/?s=NE5dypTdFo>) within 24 hours of becoming aware of the event. The Chief or Principal Investigator will respond to any SAE queries raised by the Sponsor as soon as possible.

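### Sections 11.2.3 to 11.3 give conflicting recording rules for listed expected complications, and the plan secures no count of the serious ones

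*Protocol*

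**What the plan says.** All references are to the protocol.

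**Exemption.** Section 11.2.3 gives a list of expected events with a rate for each. They are to be noted in the medical records but "do not need an Adverse Event CRF to be submitted". Section 11.2.4 adds: "Expected adverse events related to RARP listed above will not require reporting". Section 11.3 requires SAEs to reach the sponsor within 24 hours, except those that the protocol exempts. None of these sentences limits the exemption to events that are non-serious or unrelated.

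**Requirement.** Section 11.2.4 continues: "All related adverse events will be recorded in the CRF until 90 days after surgery". It then says: "All related adverse events will also be recorded on the non-CTIMP Adverse Event (AE) log". Section 11.3 says: "All serious adverse events related to the intervention will be recorded in the medical records and the CRF, and the sponsor's SAE log". None of these sentences excepts listed events. Section 11.2 has every adverse event assessed for severity, causality, seriousness and expectedness.

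**Relatedness.** Section 11.2.2 counts an event as related when a causal link with the intervention cannot be ruled out. The adverse-event section does not say whether the intervention is the LaserSAFE imaging, the secondary resection, the modified incision or the whole operation.

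**Oversight.** Section 12.1 has the Trial Management Group (TMG) review SAEs. Section 14 has sites email their adverse event log to the sponsor.

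**The concern.** The exemption and the requirement overlap. Site staff completing the form for a listed event judged related have one instruction to record it and another saying that no form is needed. Sites may resolve this differently, and the resulting counts would then not be comparable between centres.

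The list is not confined to minor events. Several items meet the SAE definition in section 11.1, for example by being life-threatening or by prolonging a hospital stay.

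Some listed items could also be affected by steps that the trial adds. Section 6.3.1.1 describes a port incision that differs from the standard operation, and re-docking of the robot. Section 6.3.1.2 describes a secondary resection reaching just past the anastomosis, which section 6.3.1.1 has the surgeon fashion while the images are being read. Section 10 names delay in finishing surgery as a risk. Wound problems, bleeding, bowel injury and anastomotic leak are all on the list.

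An excess of common surgical events is seldom recognised by judging cases one at a time. It shows in aggregate counts, and the plan does not secure these.

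**Working it through.** **Step 1. Apply the rules under each meaning of the intervention.**

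| Meaning of the intervention | Typical listed event | Rule under 11.2.3 and first rule of 11.2.4 | Rule under rest of 11.2.4 and 11.3 |
|---|---|---|---|
| Includes the prostatectomy | Related, since a link cannot be ruled out | No AE CRF, no reporting | CRF and AE log; if serious, SAE log as well |
| LaserSAFE imaging only | Usually judged not related | No AE CRF, no reporting | Not captured: these rules cover related events only |

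Under the first meaning the two rules collide routinely. Under the second they rarely collide, but most listed events are then held only in the medical records. A serious event that is unrelated and unlisted would still go to the sponsor under 11.3; a listed one would not.

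**Step 2. Number exposed.** Section 9.3 gives 693 participants, and the figure reproduces:
- 1.96² × 0.91 × 0.09 / 0.05² = 125.85, rounded up to 126 margin-positive participants
- 126 / 0.20 = 630
- 630 × 1.10 = 693

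**Step 3. Expected serious listed events.** The rates are those in 11.2.3. Which items count as serious is read from their wording.

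| Item | Rate | Expected in 693 |
|---|---|---|
| Bleeding requiring transfusion | 1% | 6.9 |
| Visceral injury requiring laparotomy | 1% | 6.9 |
| Vascular injury requiring laparotomy | 1% | 6.9 |
| Myocardial infarction | 0.1% | 0.7 |
| Deep vein thrombosis or pulmonary embolus | 0.8% | 5.5 |
| Intensive-care admission | 2% | 13.9 |
| Ileus or bowel damage (one combined line) | 0.5% | 3.5 |
| **Sum** | **6.4%** | **44.4** |

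693 × 0.064 = 44.35, about 44 events. On the 630 evaluable participants, 630 × 0.064 = 40.3.

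**Step 4. Sensitivity to what is called serious.**
- Narrow set (two laparotomy lines, myocardial infarction, intensive care): 1 + 1 + 0.1 + 2 = 4.1%; 693 × 0.041 = 28.4.
- Wider set (the 6.4% plus anastomotic leak at 5%): 11.4%; 693 × 0.114 = 79.0.

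These are counts of events. One man may have more than one.

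**The case against.** The strongest reply is that the passages can be read together. Section 11.2.4 exempts expected events related to the prostatectomy, relatedness elsewhere is to the intervention, and the only intervention named in the section 10 risk table is the LaserSAFE procedure. Background surgical events would then be exempt and LaserSAFE events recorded. This reading is not secure. Section 11.2.3 calls the listed events expected for the trial treatment, and it checks SAEs already suspected to be related against that same list, so a listed event can be a related one. Even if the reading is accepted, a serious event after the modified incision, re-docking or secondary resection that is put down to the prostatectomy reaches no stated CRF or log.

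Three further points stand in part:
- The CRF is not at hand. Section 9.6.1 says that it sets out the variables registered at the intervention, so it may already hold some complications. The claim is therefore that the protocol does not secure a count, not that none will exist.
- Lighter reporting is deliberate. Section 11.2 cites site workload and section 14 classes the study as low risk. That supports relief from expedited reporting more than it supports leaving events off the CRF.
- There is no control arm, the listed rates carry no source, and men who have a secondary resection differ in tumour extent. Counts could prompt a review but could not by themselves show an effect of LaserSAFE.

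A reader might also infer that the 90-day limit is contradictory, since 11.2 justifies it "as it unlikely any SAEs past this point will be related to surgery" while 11.2.3 has a heading "Expected longer term outcomes or side effects of surgery". The documents do not support this. Urethral stricture and incisional hernia are listed as early post-operative. The window is the same in 6.4.1, 11.2 and 11.2.4, and Appendix 1 agrees with it. The listed longer-term effects are largely followed to 12 months through EPIC-26 and the record of secondary treatments.

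**Conclusion.** The concern holds as an unresolved conflict between recording rules, together with a gap for listed events not judged related. About 44 events that are serious by their wording are expected in 693 men at the protocol's own rates (28 to 79 on narrower and wider readings of serious), and the plan secures no count of them. The figure assumes that the listed rates apply to this cohort and takes the combined bowel line at its full 0.5%.

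A reader might go further and infer that these complications escape all recording and that the TMG is blind to them. The text does not support that. Taken alone, section 11.3 puts related serious events in the CRF and SAE log, section 11.2.4 puts related events on the adverse event log, and that log goes to the sponsor. What fails is that another rule releases sites from the form for the same events, and nothing says which rule prevails.

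**What to change.** 1. In section 11, define the intervention, stating whether it covers the LaserSAFE imaging, the modified incision and the secondary resection.
2. Reconcile 11.2, 11.2.3, 11.2.4 and 11.3 so that being on the expected list exempts an event from 24-hour sponsor reporting only, not from CRF recording.
3. State that a listed event judged related to a trial-specific step is not exempt.
4. Within the existing 90-day window, record each listed event as a yes/no eCRF item with its date and whether a secondary resection was done. The medical record review scheduled in section 6.3.1, Table 2 can supply this.
5. Give the TMG descriptive counts against the listed rates, with a note that any split by secondary resection is confounded by tumour extent.

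The cost is a few minutes of data entry per participant. No visit is added and the collection window does not change.

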11.2.4. Recording of Adverse Events

All adverse events will be recorded in the medical records in the first instance. Expected adverse events related to RARP listed above will not require reporting. All related adverse events will be recorded in the CRF until 90 days after surgery.

All related adverse events will also be recorded on the non-CTIMP Adverse Event (AE) log, and stored in the site files.

11.3. Procedures for Recording and Reporting Serious Adverse Events (SAEs)

All serious adverse events related to the intervention will be recorded in the medical records and the CRF, and the sponsor's SAE log. The AE and SAE logs will be stored in the TMF Investigator Site File and may be subject to Sponsor monitoring and auditing.

Participants will be followed up until clinical recovery is complete and laboratory results have returned to normal or baseline values, or until the event has stabilised. Follow-up will continue after completion of protocol treatment and/or trial follow-up if necessary.

All SAEs (except those specified in the protocol as not requiring reporting to the Sponsor) will be reported to the Sponsor within 24 hours of becoming aware. The CI/PI or designated individual will complete the Sponsor's online Research Incident Reporting Form (<https://redcap.slms.ucl.ac.uk/surveys/?s=NE5dypTdFo>) within 24 hours of becoming aware of the event. The Chief or Principal Investigator will respond to any SAE queries raised by the Sponsor as soon as possible.

11.4. Incidental Findings in Research

Should any incidental findings be identified during the pre-operative assessment, operative procedure, or postoperative care phases of the study, these will be managed in accordance with each participating centre's standard clinical pathway. Participants will be informed of any such findings and referred for appropriate clinical management as per local protocols. However, given

that the LaserSAFE intervention specifically analyses the posterolateral prostatic margins during radical prostatectomy, and all participants are undergoing standard-of-care surgical treatment with established pre-operative imaging and postoperative follow-up, no incidental findings directly related to the study intervention are anticipated. All research staff must follow participating sites' incidental findings policies, and training will be provided as part of initiation to the research study

11.5. Protocol Deviations and Violations

Protocol Violations

A reportable protocol violation is defined as a breach which is likely to affect to a significant degree: (a) the safety or physical or mental integrity of the participants of the trial; or (b) the scientific value of the trial.

The Sponsor must be notified immediately of any protocol violations during the trial conduct phase by completion of the online JRO Research Incident Reporting Form:

<https://redcap.slms.ucl.ac.uk/surveys/?s=NE5dypTdFo>. All protocol violations must be recorded on the Protocol Violation Log and filed in the site file. Sites will additionally follow their Trust incident reporting mechanisms.

Examples of protocol violations include:

1. Not following the secondary resection criteria based on LaserSAFE results
2. Failure to communicate LaserSAFE information to the surgeon

Protocol Deviations

Protocol deviations are minor unintended departures from the expected conduct of the study protocol or Standard Operating Procedures (SOPs) which do not impact participant safety or compromise the integrity of the study data. Protocol deviations will not be reported to the Sponsor but must be recorded in the Protocol Deviation Log and filed in the site file.

Examples of protocol deviations include:

- Patient does not complete a questionnaire or completes it outside the specified time window
- Minor administrative errors that do not affect data integrity or participant safety

11.6. Reporting incidents involving a medical device

Any adverse incident involving the Histolog confocal microscope will be reported to the study coordinator and manufacturer within 24 hours of occurrence. This includes equipment faults, malfunctions, or any safety or quality issues identified during use of the device. The manufacturer, SamanTree Medical SA, will provide technical service support to the site as required. Incidents involving the Histolog confocal microscope do not require reporting to the Medicines and Healthcare products Regulatory Agency (MHRA). However, local Trust reporting procedures for medical device events must also be followed, and it is the responsibility of the Principal Investigator and study site

team to ensure they are aware of and comply with any specific local requirements for reporting device incidents.

11.7. NHS Serious Incidents and Near Misses

A serious incident or near miss is any unintended or unexpected event that could have or did lead to harm, loss or damage that contains one or more of the following components:

- a. It is an accident or other incident which results in injury or ill health.
- b. It is contrary to specified or expected standard of patient care or service.
- c. It places patients, staff members, visitors, contractors or members of the public at unnecessary risk.
- d. It puts the Trust in an adverse position with potential loss of reputation.
- e. It puts Trust property or assets in an adverse position or at risk.

Serious Incidents and near misses will be reported to the Sponsor and Trust Quality & Safety department as soon as the study team becomes aware of them.

11.8. Complaints from research participants

In the first instance, research participant complaints (patients or health volunteers) will be reported to the CI/PI to investigate, as documented in the patient information sheet(s), and to the Sponsor via [contact], following the *UCL Complaints from Research Subjects about UCL Sponsored Studies and Trials* policy. For participants who are NHS patients, complaints will be reported to the NHS Complaints Manager at the Trust where the recruitment and study procedures were undertaken. Complaints from NHS patients are handled under NHS complaints policies and procedures, with involvement from PALS and the Sponsor where necessary.

12. OVERSIGHT COMMITTEES

12.1. Trial Management Group (TMG)

The TMG will include the Chief Investigator and trial staff. The TMG will be responsible for overseeing the trial. The group will meet monthly and will send updates to PIs.

The TMG will review recruitment figures, SAEs and substantial amendments to the protocol prior to submission to the REC. All PIs will be kept informed of substantial amendments through their nominated responsible individuals.

13. REGULATORY REVIEW AND PATIENT AND PUBLIC INVOLVEMENT

13.1. Regulatory Review

The Sponsor will ensure that the trial protocol, participant information sheet, consent form, GP letter and submitted supporting documents have been approved by the appropriate research ethics committee, prior to any participant recruitment. The protocol, all other supporting documents including and agreed amendments, will be documented and submitted for ethical and regulatory approval as required. Amendments will not be implemented prior to receipt of the required approval(s).

The study was deemed to require regulatory approval from the following bodies (REC Favourable Opinion and HRA Approval). **Before any site can enrol patients into the study**, the Chief Investigator/Principal Investigator or designee will ensure that the appropriate regulatory approvals have been issued, and NHS Confirmations of Capacity and Capability and Sponsor green lights are in place.

For any amendments to the study, the Chief Investigator or designee, in agreement with the Sponsor, will submit information to the appropriate body in order for them to issue approval for the amendment. The Chief Investigator or designee will work with sites (R&D departments as well as the study delivery team) to confirm ongoing Capacity and Capability for the study.

All correspondence with the Sponsor, REC and HRA will be retained. The Chief Investigator will notify the Sponsor and REC of the end of the study.

It is the Chief Investigator's responsibility to produce the annual progress reports when required; an annual progress report (APR) will be submitted to the Sponsor and REC within 30 days of the anniversary date on which the favourable opinion was issued, and annually until the study is declared ended.

Within 90 days after the end of the trial, the CI will ensure that the main REC is notified that the trial has finished. If the trial is terminated prematurely, those reports will be made within 15 days after the end of the trial.

Within one year after the end of the study, the Chief Investigator will submit a final report with the results, including any publications/abstracts, to the Sponsor and to the REC and HRA.

